### Definitions

Evaluation of best overall response: The best overall response is the best response recorded from the start of treatment until disease progression, as defined in Table 12.3.

Evaluable for toxicity: All patients who receive at least one dose of study therapy will be evaluable for toxicity which will be assessed according to CTCAE v4.0 as well as by documentation of dose delay/adjustments that are required.

Evaluable for objective response: All patients who receive at least one dose of study therapy will be included in the modified intent-to-treat analysis of efficacy. Patients who come off study for any reason prior to the first radiographic tumor assessment will be treated as having progressive disease.

Evaluable for primary/secondary objectives: In order to be considered eligible for the primary and secondary objectives described in this study, patients must receive (1) at least one dose of study therapy and remain on study until at least the first radiographic tumor assessment (week 6) or (2) at least one dose of study therapy and have clear clinical or radiographic progression prior to the planned first radiographic tumor assessment at week 6. Patients who come off study for reasons other than clinical/radiographic progression prior to the first radiographic tumor assessment will be replaced.

Progression free survival (PFS) is defined as the duration of time from beginning study therapy (C1D1) to time of progression or death, whichever occurs first. Clinical deterioration consistent with progressive disease in absence of radiographic evidence of progression (“clinical progression”) will be considered progression for purposes of determining PFS. In patients who continue on study therapy after an initial scan demonstrates progressive disease, if repeat scans confirm PD, then progression should be declared using the date of the initial scan. If repeat scans do not confirm PD, then the subject will not be considered to have progression at the initial scan. Patients who enroll but do not receive any study therapy will not be included in the PFS analysis. Patients who started a

subsequent anti-cancer therapy without a prior reported progression will be censored at the last evaluable tumor assessment prior to initiation of the subsequent anti-cancer therapy. Patients who discontinue from therapy and withdraw consent for follow-up without a prior reported progression will also be censored at the last evaluable tumor assessment prior to withdrawal of consent.

Overall survival (OS) is defined as the duration of time from beginning study therapy (C1D1) to time of death. Patients who enroll but do not receive any study therapy will not be included in the OS analysis.

### 13.0 CRITERIA FOR REMOVAL FROM STUDY

Nivolumab and ipilimumab treatment should be permanently discontinued for the following reasons and the specific reasons for removal from study will be documented:

- Patient withdrawal of consent at any time
  - Every effort should be made to obtain information on patients who withdraw from the study. The primary reason for withdrawal from the study should be documented. However, patients will not be followed for any reason after consent has been withdrawn.
- Termination of the study by MSKCC or BMS for any reason
- Radiographic progression: Confirmed disease progression per RECIST v1.1.
  - Patients who experience initial progressive disease may continue therapy if they are experiencing clinical benefit. A CT scan should be repeated no more than 6 weeks after the first documentation of progressive disease. If there is at least 10% more progression (e.g. first scan showed 24% growth relative to baseline, second scan shows 36% growth relative to baseline), then study therapy should be discontinued. If, instead, <10% further progression is seen, the patient may continue study therapy until confirmed progression of disease so long as there is continued clinical benefit.
- Clinical progression: Symptomatic deterioration attributed to disease progression as determined by the investigator after integrated assessment of radiographic data, biopsy results, and clinical status.
- Other conditions: Any medical condition that may jeopardize the patient's safety if he or she continues on study treatment.
- Pregnancy
- New therapies: Use of another systemic anti-cancer therapy.
  - Cases in which patients experience a mixed response requiring local therapy (e.g. surgery, stereotactic radiosurgery, radiotherapy, radiofrequency ablation) for control of tumor growth or symptoms may still be eligible to continue study treatment so long

as such therapy is not directed at a target lesion used for assessment of radiographic progression per RECIST v1.1 Such cases must be discussed with and approved by the Sponsor-PI.

Certain toxicities, specific to each drug: The assessment for discontinuation of nivolumab should be made separately from the assessment made for discontinuation of ipilimumab. Although there is overlap among the discontinuation criteria, if discontinuation criteria are met for ipilimumab but not for nivolumab, treatment with nivolumab may continue if ipilimumab is discontinued. If a subject in any of the nivolumab/ipilimumab combination arms meets criteria for discontinuation and investigator is unable to determine whether the event is related to both or one study drug, the subject should discontinue both nivolumab and ipilimumab and be taken off the treatment phase of the study.

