#### Treatment beyond Disease Progression:

Accumulating evidence indicates a minority of subjects treated with immunotherapy may derive clinical benefit despite initial evidence of PD (115). Subjects treated with nivolumab plus ipilimumab will be permitted to continue nivolumab plus ipilimumab treatment beyond initial RECIST 1.1 defined PD, assessed by the investigator, as long as they meet the following criteria:

- Investigator-assessed clinical benefit, and do not have rapid disease progression.
- Tolerance of study drug
- Stable performance status
- Treatment beyond progression will not delay an imminent intervention to prevent serious complications of disease progression (e.g., CNS metastases)
- Subject provides written informed consent prior to receiving additional nivolumab treatment acknowledging the possibility of any reasonably foreseeable risks or discomforts, as well as the possibility of alternative treatment options.

The assessment of clinical benefit should take into account whether the subject is clinically deteriorating and unlikely to receive further benefit from continued treatment.

If the investigator feels that the nivolumab plus ipilimumab subject continues to achieve clinical benefit by continuing treatment, the subject should remain on the trial and continue to receive monitoring according to the Study Calendar in Section 10.0. A radiographic assessment/CT scan should be performed no earlier than 4 weeks after original PD to determine whether there has been a decrease in the tumor size or continued PD.

For the subjects who continue nivolumab plus ipilimumab study therapy beyond progression, further progression is defined as an additional 10% increase in tumor burden compared to baseline above the degree of progression determined at the time of initial PD (e.g. if progression of disease is determined with 24% growth from baseline and a subsequent confirmatory scan shows 33% growth compared to baseline (but 9% growth compared to initial PD) patient can continue on therapy. However, if there is 36% growth compared to baseline (and 12% growth compared to initial PD, patient should be discontinued from study treatment). This includes an increase in the sum of diameters of all target lesions and/or the development of new measurable lesions.

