#### Palliative Local Therapy

Palliative local therapy, including palliative (limited-field) radiation therapy and palliative surgical resection, is permitted prior to discontinuation of study treatment if the following criteria are met:

- 1) The subject is considered to have clinically or radiographically progressed at the time of palliative local therapy and meets criteria to continue with treatment beyond progression in the section above.
- 2) The lesion planned for palliative local radiation is not a target lesion used for assessing radiographic response
- 3) The case is discussed with the PI-Sponsor prior to the initiation of palliative local therapy. Palliative therapy must be clearly documented as such in the study record.

The potential for overlapping toxicities with radiotherapy and nivolumab plus ipilimumab currently is not known. If palliative radiotherapy is required for a tumor lesion, study therapy should be withheld for at least 1 week before, during, and 1 week after radiation. Subjects should be closely monitored for any potential toxicity during and after receiving radiotherapy, and AEs should resolve to Grade ≤ 1 prior to resuming nivolumab or ipilimumab.

Follow-up Assessments after Last Dose of Study Treatment

Patients will be followed for safety for 100 days following their last dose of study treatment. Patients who have an ongoing study-treatment related adverse event at the time of study completion or at discontinuation from the study will be followed until one of the following occurs: the event has resolved to baseline grade, the event is assessed by the study doctor as stable, new anti-cancer treatment is initiated, the patient is lost to follow-up, the patient withdraws consent, or it has been determined that the study treatment or participation was not the cause of the AE.

All patients will be followed for survival and subsequent anti-cancer therapy approximately every 3 months until death, loss to follow-up, or study termination.

End of Study

The end of study is defined as the date of the last follow-up visit of the last patient enrolled and is expected to occur approximately 4 months after the last patient enters the study.

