**Complete Response (CR):** Disappearance of all non-target lesions. All lymph nodes must be non-pathological in size (< 10 mm short axis).

**Non-CR/Non-PD:** Persistence of one or more non-target lesion(s) above the normal limits.

**Progressive Disease (PD):** Unequivocal progression of existing non-target lesions (Note: the appearance of one or more new lesions is also considered progression). To achieve ‘unequivocal progression’ on the basis of the non-target disease, there must be an overall level of substantial worsening in non-target disease such that, even in presence of SD or PR in target disease, the overall tumor burden has increased sufficiently to merit discontinuation of therapy. A modest ‘increase’ in the size of one or more non-target lesions is usually not sufficient to qualify for unequivocal progression status.

Confirmation of Scans

**Verification of Response:** Initial observations of response will be confirmed by repeat scans which should be performed no earlier than 4 weeks after the original observation to ensure that responses identified are not the result of measurement error. After an initial PR or CR is noted, the subsequent protocol-specified tumor assessment may serve as the confirmation.

**Verification of Progression:** Progression of disease should be verified in cases where progression is equivocal. If repeat scans confirm PD, then progression should be declared using the date

of the initial scan. If repeat scans do not confirm PD, then the subject is considered not to have progressive disease per RECIST 1.1.

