#### Best Overall Response:

The best overall response is determined once all the data for a subject is known. It is defined as the best response designation recorded between the date of first treatment and the date of objectively documented progression per RECIST v1.1 or the date of initiating subsequent therapy, whichever occurs first. For subjects without documented progression or subsequent therapy, all available response designations will contribute to the BOR assessment. The subjects best overall response assignment will depend on the findings of both target and non-target disease and will also take into consideration the appearance of new lesions.

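### Section 9 bars on-study local treatment of a target lesion for radiation only, so resecting one before the repeat scan can cancel a PFS progression event with no drug effect

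*Combined protocol and SAP*

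**What the plan says.** Two sections govern local therapy during study treatment.

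- Section 9, Palliative Local Therapy, says that such therapy, "including palliative (limited-field) radiation therapy and palliative surgical resection, is permitted prior to discontinuation of study treatment", subject to three criteria. The patient must be regarded as already progressed and must qualify for treatment beyond progression. Criterion 2 reads: "The lesion planned for palliative local radiation is not a target lesion used for assessing radiographic response". The case must be discussed beforehand with the PI-Sponsor.
- Section 13, under new therapies, deals with a mixed response that needs local treatment. It names surgery along with radiosurgery, radiotherapy and ablation. Study treatment may go on provided that "such therapy is not directed at a target lesion used for assessment of radiographic progression per RECIST v1.1", with Sponsor-PI approval.

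Two rules fix when the repeat scan is done. Section 9, Treatment beyond Disease Progression: "A radiographic assessment/CT scan should be performed no earlier than 4 weeks after original PD". Section 13: "A CT scan should be repeated no more than 6 weeks after the first documentation of progressive disease".

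Section 12 says what the repeat scan does. For PFS in patients who continue study therapy after a first PD scan, the Definitions state: "If repeat scans do not confirm PD, then the subject will not be considered to have progression at the initial scan". The paragraph on continuing treatment despite radiographic PD agrees, dating progression to the first scan only if a later one confirms it. Under Verification of Progression there is a similar rule, "If repeat scans do not confirm PD, then the subject is considered not to have progressive disease per RECIST 1.1", but that paragraph opens by asking for verification where progression is equivocal.

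Section 12 has rules for lesions that split or merge, that become too small to measure, or that lie in a previously treated area. It has none for a target lesion resected on study.

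**The concern.** The target-lesion criterion exists so that local treatment does not alter the measurements by which the drug is judged. In Section 9 it covers radiation but not surgery, which alters the sum of diameters most directly. A resection in the weeks between the first PD scan and the repeat scan can shrink the sum, and the repeat scan then fails to confirm PD.

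The quantity at stake is PFS. The event at the first scan is lost, and the patient stays at risk until a later progression or death, or is censored. PFS in that patient is lengthened by surgery. Section 14 uses PFS only in a Cox regression on mutational burden that may be performed, so the reach is limited. With 30 patients, however, single events carry weight.

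**Working it through.** **Scale.** Section 9 gives an example of further progression: 24% growth followed by 33% or 36%, described as 9% and 12% more. 33 − 24 = 9 and 36 − 24 = 12, so the protocol works in percentage points of the baseline sum. (Relative to the PD scan the figures would be 1.33/1.24 − 1 = 7.3% and 1.36/1.24 − 1 = 9.7%.) Below, the baseline sum is 1 and the sum at first PD is 1.24.

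**Which patients are exposed.**

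| Patient progressed, target lesion to be resected | Section 9 | Section 13 |
|---|---|---|
| Other lesions shrinking (mixed response) | not barred | drug may not continue |
| Other lesions stable or growing | not barred | mixed-response clause does not clearly apply |

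In the first row Section 13's express condition settles the matter. The second row is open.

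**Timing.** The repeat scan falls 4 to 6 weeks after first PD. No rule keeps surgery out of that interval.

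**Lesion scored 0.** Assume the remaining lesions are unchanged between the two scans and that confirmation means the sum is still at least 20% above baseline (Table 12.1). PD is unconfirmed once the sum is below 1.20. The share of the current sum that must be removed exceeds

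1 − 1.20/1.24 = 0.04/1.24 = 3.2%, or 4% of the baseline sum.

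**Lesion dropped from both sums.** Let b be the lesion's baseline size and L its size at first PD, as fractions of the baseline sum. PD is unconfirmed if (1.24 − L)/(1 − b) < 1.20, that is, L > 0.04 + 1.20b. This holds when the resected lesion is the one driving the growth.

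**Illustration (sizes assumed; other lesions stable, so not a mixed response).** Five target lesions of 20 mm, baseline 100 mm. At first PD one measures 44 mm and four measure 20 mm: 124 mm, +24%. The 44 mm lesion is resected.

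- Carried forward at its last size: 124/100, +24%, PD confirmed.
- Scored 0: 80/100, −20%, stable disease, PD not confirmed.
- Dropped from both sums (b = 0.20, L = 0.44, and 0.44 > 0.04 + 0.24 = 0.28): 80/80, 0%, stable disease, PD not confirmed.

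Only carrying the lesion forward keeps the event, and Section 12 does not choose among the three.

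**Partial response.** With the lesion scored 0, the sum must fall to 0.70. The share removed must be at least (1.24 − 0.70)/1.24 = 0.54/1.24 = 43.5% of the current sum. In the illustration it is 44/124 = 35.5%, so the event is lost but no response is created.

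**The case against.** Section 9's silence on surgery can be read together with Section 13's express condition, so that target lesions are protected throughout. Section 9 also requires that the patient already be regarded as progressed, excludes rapid progression, and requires prior discussion with the PI-Sponsor. These points make the event less likely. They do not close the gap: Section 13's clause is written for mixed responses, discussion sets no scoring rule, and being regarded as progressed does not override a PFS definition that later withdraws the progression.

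If confirmation instead means a further 10% of growth, stable lesions leave PD unconfirmed without any surgery. The 3.2% figure therefore belongs to the +20% reading only. PD based on new or non-target lesions is not undone by resecting a target lesion, and clinical progression counts for PFS without a repeat scan.

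A reader might go further and infer that such a patient becomes a false RECIST responder in the primary comparisons. With assumed lesions of 40, 30 and 30 mm growing to 64, 30 and 30 mm (+24%), resecting the first and scoring it 0 gives 60/100, or −40%. The documents do not support treating this as the expected result:

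- The instruction to record 0 is written for lesions too small to measure. The rule on lesions with prior local treatment is closer, and points away from measurability.
- The broad cancellation rule sits in the PFS definition. Best response closes at "the date of objectively documented progression per RECIST v1.1" (or at subsequent therapy), and the verification rule in the response section is tied to equivocal PD.
- Section 12 classes shrinkage after RECIST progression as irPR or irCR, which enters no Section 14 analysis.
- Section 14 counts a response at any time on nivolumab, but does so under RECIST criteria and need not override the best-response window.
- If other lesions are shrinking, Section 13 already stops the drug.
- A PR would also need a dominant lesion removed, no new lesions or non-target PD, and a confirming scan.

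**Conclusion.** The concern holds for PFS. Section 9 leaves surgery outside its target-lesion criterion, and Section 12 as written lets a resection before the repeat scan cancel a radiographic PD. At 24% growth, removing more than 3.2% of the current sum is enough if the lesion is scored 0. If it is dropped from both sums, the event is also lost when that lesion drove the growth. Both results assume that the other lesions are unchanged and that confirmation means still at or above +20%.

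A false partial response is possible only on a stretched reading and with about 43.5% of the current sum removed. For scale, if 9 of 30 patients respond (an assumption based on the roughly 30% response rate cited in Section 2), one such case moves 30.0% (exact 95% CI 14.7 to 49.4) to 33.3% (17.3 to 52.8).

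The documents give no frequency; it is probably low and may be zero. The study describes itself as descriptive and exploratory. Severity is minor.

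**What to change.** 1. In Section 9, Palliative Local Therapy, widen criterion 2 from radiation to any palliative local therapy (radiation, surgery or ablation), so that it matches Section 13.
2. Add to Section 12: if a target lesion nevertheless receives local therapy on study, any earlier PD stands, and a fall in the sum caused by its removal can neither un-confirm PD nor count toward CR or PR.

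The cost is one reworded criterion and one added sentence. No patients, scans, data fields or analyses are added.

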**Nivolumab dose discontinuation:**

- Any Grade 2 drug-related uveitis, eye pain or blurred vision that does not respond to topical therapy and does not improve to Grade 1 severity within the re-treatment period OR requires systemic treatment
- Any Grade 3 non-skin, drug-related adverse event lasting > 7 days, with the following exceptions for laboratory abnormalities, drug-related uveitis, pneumonitis, bronchospasm, hypersensitivity reactions, infusion reactions, and endocrinopathies:
  - Grade 3 drug-related uveitis, pneumonitis, bronchospasm, hypersensitivity reaction, or infusion reaction of any duration requires discontinuation
  - Grade 3 drug-related endocrinopathies adequately controlled with only physiologic hormone replacement do not require discontinuation
  - Grade 3 drug-related laboratory abnormalities do not require treatment discontinuation except:
    - Grade 3 drug-related thrombocytopenia > 7 days or associated with bleeding requires discontinuation
    - Any drug-related liver function test (LFT) abnormality that meets the following criteria requires discontinuation:
      - AST or ALT > 10x ULN
      - AST or ALT > 5-10x for > 2 weeks
      - Total bilirubin > 5x ULN
      - Concurrent AST or ALT > 3x ULN and total bilirubin > 2x ULN
- Any Grade 4 drug-related adverse event or laboratory abnormality, except for the following events which do not require discontinuation:
  - Grade 4 neutropenia ≤ 7 days
  - Grade 4 lymphopenia or leukopenia
  - Isolated Grade 4 amylase or lipase abnormalities that is not associated with symptoms or clinical manifestations of pancreatitis.
  - Isolated Grade 4 electrolyte imbalances/abnormalities that are not associated with clinical sequelae and are corrected with supplementation/appropriate management within 72 hours of their onset
  - Grade 4 drug-related endocrinopathies adequately controlled with only physiologic hormone replacement do not require discontinuation

- Any event that leads to delay in dosing lasting > 6 weeks from the previous dose requires discontinuation, with the following exceptions:
  - Dosing delays to allow for prolonged steroid tapers to manage drug-related adverse events are allowed. Tumor assessments should continue as per protocol even if dosing is delayed.
  - Dosing delays lasting > 6 weeks from the previous dose that occur for non-study-drug-related reasons may be allowed. Tumor assessments should continue as per protocol even if dosing is delayed.
- Any adverse event, laboratory abnormality, or intercurrent illness which, in the judgment of the Investigator, presents a substantial clinical risk to the subject with continued nivolumab dosing.

